##### **Cohort A specific inclusion criteria – High risk primary PCa**

8. Unfavourable intermediate-risk or high-risk PCa defined by NCCN Guidelines Version 2.2019 (clinical stage  $\geq$ T2b or PSA  $>10$  ng/mL or Gleason score  $\geq 4 + 3 = 7$ ).
9. Scheduled for radical prostatectomy with or without pelvic lymph node dissection.

##### **Cohort B specific inclusion criteria - Hormone sensitive metastatic PCa**

10. Castration-naïve metastatic PCa with a known number of metastases or a high likelihood of lymph node metastases and/or bone metastases.
11. Either clearly demonstrated disease by site standard of care imaging performed as part of the subject's routine clinical work-up within 12 weeks before enrolment or biochemical recurrence with a PSA  $< 15$  ng/mL.

##### **Cohort C specific inclusion criteria– Castration resistant metastatic disease**

12. A quantifiable number or a high likelihood of metastases, either documented by standard of care imaging performed as part of the subject's routine clinical work-up within 12 weeks before enrolment or by biochemical progression (see 14a).
13. Ongoing androgen deprivation with luteinizing hormone-releasing hormone (LHRH) agonist/antagonist therapy or bilateral orchiectomy.
14. Castrate serum testosterone  $< 50$  ng/dL or 1.7 nmol/L plus either;
  - a. Biochemical progression: Three consecutive rises in PSA at least one week apart resulting in two 50 % increases over the nadir, and a PSA  $> 2$  ng/mL or,

b. Radiological progression: The appearance of new lesions: either two or more new bone lesions on bone scan or soft tissue lesion(s) progression using RECIST (Response Evaluation Criteria in Solid Tumours).

#### 4.6 Exclusion criteria - Patients with Prostate Cancer

##### **All Patient Cohorts**

1. A biopsy has been obtained from the prostate within the 28 days before enrolment.
2. Patients with extensive metastatic disease (more than 20 lesions).
3. Patients with a second primary cancer or any other underlying disease which might confound interpretation of the study results.
4. The subject has had any major surgery within 2 months prior to screening.
5. The subject has bilateral hip prostheses.
6. The subject has received, or is scheduled to receive, Ga-PSMA-11 or F-PSMA-1007 from 1 month before to 1 week after administration of F-rhPSMA-7.3, or any other IMP from 3 months before to 1 week after administration of F-rhPSMA-7.3.
7. The subject has a history of alcohol or drug abuse within the previous 12 months, based on a review of medical records or other available evidence.
8. The subject has known hypersensitivity to F-rhPSMA-7.3 injection or any of its constituents.
9. Subjects administered any high energy (>300 keV) gamma-emitting radioisotope within five physical half-lives, or any i.v. iodinated contrast medium within 24 hours, or any high density oral contrast medium (oral water contrast is acceptable) within 5 days, prior to study drug administration.
10. Subjects who have recently received an x-ray contrast agent (<24 hr for i.v. agents and <5 days for oral agents).
11. Subjects with a history of claustrophobia or panic attacks when in confined spaces.

##### **Cohort A and B specific exclusion criteria**

12. The subject is being treated or has been treated for PCa with chemotherapy or radiation therapy.
13. Patients currently receiving or with a prior history of hormonal treatment/androgen deprivation therapy including bilateral orchiectomy.

##### **Cohort C specific exclusion criteria**

14. Radiation therapy for treatment of any metastatic lesions in the field of view of the dynamic images.

#### 4.7 Recruitment

CRST has a data bank of healthy volunteers, which will be screened for suitable candidates. In addition, volunteers may be recruited by advertising in newspapers, via mailing lists, internet pages and bulletin boards. Interested persons are advised to call or contact by e-mail the person responsible for subject recruitment. Subjects with PCa are recruited from the clinics of Urology and Oncology of Turku University Hospital.

At first, the study is briefly described to the subject candidate in layman's language. The candidate is told that the information gained in this discussion is collected on a study-specific interview form. The name, date of birth and contact information of the candidate are recorded on the interview form. Next, the main inclusion and exclusion criteria are checked. If an exclusion criterion is fulfilled, this is immediately told to the candidate, and the interview is ended with possible health-related instructions. If the candidate might be suitable for the study, the procedures for providing the study ICF are discussed, and the next steps in the recruitment procedure are agreed upon. Upon the subject candidate's agreement, a screening visit may be booked. The ICF is sent to the candidate by post, e-mail or another method. A subject can only be enrolled into the study after a sufficient consideration period.

#### 4.8 Instructions concerning lifestyle and concomitant treatments

1. Alcohol intake is prohibited during 48 hours before the IMP administration/PET scan visit.
2. The subjects will have to fast for at least 4 hours before the screening visit and the IMP administration/PET scan.
3. Subjects should be well-hydrated before the IMP administration (e.g. oral intake of 500 mL of water during a 2 hour period prior to IMP administration).
4. Strenuous physical exercise is not allowed in the 48 hours before the screening and IMP administration/PET scan visits, and until 24 hours after IMP administration.
5. For instructions regarding prior and concomitant treatments, please see Section 5.4.
6. Subjects will be instructed to report all prior and concomitant medications and possible AEs to the study personnel.

#### 4.9 Withdrawal and replacement of subjects

The Investigator may withdraw a subject from the study at any time based on the Investigator's clinical judgement. A subject will be withdrawn from the trial prematurely if an AE jeopardising her/his well-being occurs, or if the discontinuation is otherwise in the best interest of the subject. A subject will also be withdrawn from the study if she/he fails to comply with the trial protocol.

A subject has the right to withdraw her/his consent without the need to justify the decision. However, every effort should be made to find out the reason for the withdrawal.

All information collected from a withdrawn subject, including the reason for withdrawal, will be included in the study file for use as study data and for purposes of verification.

Once withdrawn, a subject cannot re-enter the study unless the withdrawal was due to scheduling reasons and the subject did not receive the IMP. It will be decided case-by-case, in joint agreement between the Investigator and the Sponsor, whether a discontinued subject will be replaced or not.

#### 4.10 Evaluability criteria and additional subjects

Healthy Volunteer Evaluability Criteria:

As it is important that the study has the required number of evaluable healthy volunteers, the following criteria will be applied, and if the healthy volunteer is not evaluable for efficacy, an additional subject may be included in the study to substitute for the non-evaluable subject:

- Completion of scanning sessions I, II and III and collection of venous blood and urine analysis (as described in the Study Imaging Manual) to be able to undertake a calculation of the subject's internal radiation dosimetry.

Patient Evaluability Criteria:

As it is important that each cohort has the required number of evaluable patients, the following criteria will be applied and if the patient is not evaluable for efficacy, an additional subject may be included in the study to substitute for the non-evaluable subject:

- Completion of scanning sessions I and II and collection of venous blood and urine analysis (as described in the Study Imaging Manual) to be able to perform kinetic modelling.
- At least one positive lesion on the F-rhPSMA-7.3 scan.
- Cohort A only: Radical prostatectomy performed within 30 days of the F-rhPSMA-7.3 scan. In case of a delay of the planned surgery by up to 2 days beyond this 30-day window, a subject may still be considered evaluable.

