## 2.4 Secondary endpoints

The secondary endpoints of the study are:

1. Dosimetry estimates and cumulated activity exposure by source region and the entire body including analysis of activity in whole blood, plasma and excreted urine in healthy volunteers.
2. Uptake of  $^{18}\text{F}$ -rhPSMA-7.3 injection visualised by PET imaging compared to histopathology in subjects with PCa, if histopathology information is available.
3. Use of kinetic modelling data to investigate distribution of  $^{18}\text{F}$ -rhPSMA-7.3 in subjects with PCa.
4. Use of kinetic modelling data to optimise the imaging protocol for future studies in subjects with PCa, by estimating *in vivo*  $^{18}\text{F}$  radioactivity in PCa lesions.
5. Analysis of % of radioactive parent compound present in plasma over time in healthy volunteers and subjects with PCa. Relative proportions of radioactive tracer metabolites will be monitored, as well, if detected in significant amounts in the radio-HPLC analysis.

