### 7.2.2 Uptake irreversibility/reversibility

Kinetics of F-rhPSMA-7.3 uptake in PCa lesions is compared to the availability of parent F-rhPSMA-7.3 in plasma by plotting SUVR of lesion and parent F-rhPSMA-7.3 in plasma, and by irreversible and reversible multiple-time graphical analyses (Patlak and Logan plots) (Logan, 2000).

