### 7.4.2 Urine sampling

Urine samples should be collected in timed fractions before the tracer injection, during the scanning break(s) and after the scan. Urine samples should be collected in the following fractions as calculated from the time of  $^{18}\text{F}$ -rhPSMA-7.3 administration: until -5 min, -5 to 95 min, 95 to 185 min and 185 to 255 min (healthy volunteers) or until -5 min, -5 to 50 min, 50 to 125 min and 125 to 240 min (patients with PCa). The collection times are approximations and will depend on actual voiding times.

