#### 8.2.3 Data sets to be analyzed

The safety analysis set (SAF) will include all subjects who received any administration of the IMP.

Evaluable Analysis set (EAS) will include subjects who met all inclusion and exclusion criteria, received IMP, underwent PET/CT scans and met the scan evaluability criteria set out in section 4.10.

Statistical analyses for the primary and secondary endpoints (besides safety) will be performed using EAS. Safety will be assessed using the safety analysis set (SAF).

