#### 8.2.6 Analysis of efficacy variables

In subjects with PCa, the lesion(s) detected on the PET images will be visually evaluated by the on-site investigator. A semi-quantitative analysis, using standardised uptake values (SUV), will be derived. SUV is a ratio of tissue radioactivity concentration and administered dose of radioactivity divided by body weight:

- SUV = activity (Bq/g)/[injected radioactivity (Bq))/body weight (g)]
- SUVmax is the maximum standardized uptake value.
- SUVmean is the mean standardized uptake value.
- SUVR is a ratio of SUV in a detected lesion and SUV of a reference tissue, such as blood.

The variables will be presented using summary statistics.

Analysis, using SUV, will be used to compare lesions seen on the PET images with lesions from histopathology results, where available. This assessment of which lesion detected on the PET images matches the lesion for which histopathology results are available will be made by the on-site investigator. As far as possible, exploratory comparisons will be made regarding:

- Gleason Scores and degree of uptake of F-rhPSMA-7.3 in primary prostate lesions
- Historical Gleason Score, PSA, PSA kinetics or other biomarkers and degree of uptake of F-rhPSMA-7.3 in metastatic lesions.

Kinetic modelling of the dynamic imaging data in patients will be used to determine the optimal imaging protocol for future studies.

The detailed results of the histopathology and immunohistochemistry analysis of the prostate specimens of the Cohort A subjects will not be entered into the eCRF, but will be reported separately for each Cohort A subject in a Histopathology and Immunohistochemistry Report to be prepared by the study pathologist and to be included as an Appendix in the Clinical Study Report. The immunohistochemistry analysis results that are to be entered into the eCRF include the following:

- Number of carcinoma lesions and their diameter
- Gleason grade/score
  - Primary, secondary and tertiary if applicable

Overall and for each separate carcinoma lesion separately

- Perineural invasion (yes/no)
- Extraprostatic extension (yes/no)
- T-class (pTNM)
- Surgical margin positivity (yes/no, location)
- Seminal vesicle invasion (yes/no)
- Lymph node status (# of metastatic/benign lymph nodes reported for each location with dissected lymph nodes)

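### Urine collection is written as a condition for patients to be evaluable for efficacy, though no kinetic or lesion analysis described uses urine, so EAS membership with incomplete urine is uncertain

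*Protocol*

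**What the plan says.** **Evaluability.** Section 4.10 of the protocol, repeated in the synopsis, asks of each patient: scanning sessions I and II, together with "collection of venous blood and urine analysis (as described in the Study Imaging Manual) to be able to perform kinetic modelling"; a positive lesion on the scan; and, in Cohort A, prostatectomy within the stated window. A patient who is not evaluable for efficacy may be substituted by an additional subject. The parallel rule for healthy volunteers also joins urine to scans and blood, but gives the dosimetry calculation as the reason.

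**Analysis set.** Section 8.2.3 admits to the EAS subjects who, besides meeting the entry criteria and receiving the product, "underwent PET/CT scans and met the scan evaluability criteria set out in section 4.10". All non-safety endpoints are analysed on the EAS.

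**Kinetic analysis.** Under 7.2.2, lesion uptake "is compared to the availability of parent" tracer in plasma, by plotting and "by irreversible and reversible multiple-time graphical analyses (Patlak and Logan plots". Section 8.2.6 adds: "Kinetic modelling of the dynamic imaging data in patients will be used to determine the optimal imaging protocol for future studies".

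**Urine.** Secondary endpoint 1 in 2.4 includes "analysis of activity in whole blood, plasma and excreted urine in healthy volunteers". Section 7.4.2 sets fractions for volunteers and for patients and notes: "The collection times are approximations and will depend on actual voiding times". Sections 7.4.4 and 8.2.9 list urinary radioactivity among the pharmacokinetic variables, for descriptive summary, without limiting it to either group.

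**The concern.** The reason given for the urine condition in patients does not match the analyses it is meant to serve. In volunteers the link is clear: dosimetry uses a dynamic bladder model (8.2.8), and the excreted-urine endpoint is theirs. For patients, the same wording appears with only the purpose changed.

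The synopsis itself lists urinary radioactivity under pharmacokinetics and not under efficacy. A pharmacokinetic sample therefore helps decide who is evaluable for efficacy.

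At stake are very small cohorts. If the condition is applied as written, a patient who supplied everything the lesion and kinetic analyses need could be left out of them. The sponsor could then enrol another patient, at the total effective dose of 9.2 mSv that section 5.1 states for patients. If the condition is read loosely, the same patient stays in. Two analysts could form different sets from the same data.

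**Working it through.** **1. The plan's own figure.** Sections 4.2 and 8.1: 6 volunteers + 3 cohorts × 3 patients = 15 evaluable subjects. This reproduces. There is no hypothesis, alpha or power (8.2.2), so no power calculation applies.

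**2. Inputs of each patient analysis, as the protocol describes them.**

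| Analysis | Section | Inputs named | Urine named? |
|---|---|---|---|
| SUVmax, SUVmean, SUVR | 7.2.1, 8.2.6 | tissue activity, injected activity, body weight, reference tissue | No |
| Reversibility, Patlak and Logan plots | 7.2.2 | lesion uptake over time, parent tracer in plasma | No |
| Kinetic modelling for the imaging protocol | 8.2.6 | dynamic images | No |
| Lesion uptake against pathology | 7.2.3, 8.2.6 | SUV, histology | No |
| Descriptive pharmacokinetics | 7.4.4, 8.2.9 | blood, plasma, urine | Yes |

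Only the last row needs urine, and it is not one of the efficacy variables.

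**3. Route from a missing fraction to the EAS.** Take a patient with both sessions, the blood samples, a positive lesion and, in Cohort A, surgery in time, who lacks one of the three post-injection fractions (-5 to 50, 50 to 125, 125 to 240 min).
- *Plain reading of 4.10:* urine is one of the joined items, he lacks part of it, so he is not evaluable. By 8.2.3 he is outside the EAS and its SUV, kinetic and histology comparisons.
- *Softer reading:* the closing purpose clause is the test. Modelling is possible without urine, so he qualifies.
- Section 8.2.3 speaks of scan criteria, and 8.1 names only the positive lesion while pointing to 4.10. Neither settles which reading applies.

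**4. Size of one exclusion.** 1/3 = 33% of a cohort, or 1/9 = 11% of all patients. This needs no assumption about rates.

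**5. Frequency.** The protocol gives no rate of urine loss. Purely as illustration, let each patient independently have incomplete urine with assumed probability q. The chance of at least one such patient is 1 − (1 − q)^n:

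| q (assumed) | n = 3 (one cohort) | n = 9 (all patients) |
|---|---|---|
| 5% | 1 − 0.95³ = 14% | 1 − 0.95⁹ = 37% |
| 10% | 1 − 0.90³ = 27% | 1 − 0.90⁹ = 61% |
| 20% | 1 − 0.80³ = 49% | 1 − 0.80⁹ = 87% |

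The table shows only how the result depends on q; it is not an estimate for this trial. With urine removed from the patient criterion, no patient can be excluded for this reason and the target of 9 is unchanged.

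**The case against.** The strongest reply is that 4.10 never says a lost fraction makes a patient non-evaluable. It asks for collection sufficient for modelling, as set out in an imaging manual that is not shown. The EAS definition refers to scan criteria, and urine is not plainly one. This stands as far as it goes: exclusion is one reading and not a certainty. But under the softer reading the word urine has no effect for patients, and the protocol does not say which reading governs.

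Several stronger conclusions might be inferred, and the protocol does not support them:

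- *That the patient's data are thrown away.* Section 8.2.4 has all collected data summarised and listed, Cohort A histology is reported for each subject in an appendix to the study report, and the safety set keeps everyone dosed.
- *That another man will be injected.* Substitution is optional.
- *That patient urine has no purpose.* It has its own collection schedule and a descriptive pharmacokinetic use. That justifies collecting it, but not making lesion analyses depend on it.
- *That no kinetic analysis could ever use urine.* The objective covers tracer distribution in general, and detail is left to a separate analysis plan. The claim here is limited to the analyses the protocol describes.
- *That urine loss will be common in men with prostate disease.* Nothing in the protocol says so. Collection times are approximate, so a late void may only shift a boundary.

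**Conclusion.** The point holds as a mismatch between a criterion and its stated purpose, with an unclear consequence for EAS membership. On the plain reading, incomplete urine alone can take a patient out of every EAS analysis, although none of the efficacy analyses described uses urine. Each such case costs 33% of a cohort and permits, but does not require, one more enrolment. On the softer reading nothing is lost.

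The conclusion rests on the analyses as described in 7.2.1 to 7.2.3 and 8.2.6, and on taking the joined items in 4.10 at face value. It does not rest on any rate of urine loss, and how often this would occur cannot be stated. The study is exploratory and descriptive, so no error rate is affected. With three patients per cohort, though, who is counted should not depend on how a clause is read.

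**What to change.** In 4.10 and in the synopsis, make the patient criterion completion of the two scanning sessions plus the venous blood samples that the kinetic modelling needs. Leave the positive-lesion and Cohort A surgery criteria as they are. Keep urine as a condition for healthy volunteers, where dosimetry is the reason. For patients, make it a condition only for entering the descriptive urine pharmacokinetic summary.

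Then align 8.1 and 8.2.3: 8.1 should refer to the full criteria and not to the positive lesion alone, and 8.2.3 should say that all the criteria of 4.10 apply, so that the word scan no longer leaves doubt.

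The cost is one phrase in two places and two small alignments. Urine is still collected. The downside is that the patient urine summary may include fewer subjects than the EAS, so its denominator should be stated.

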### 30 Day Follow-up:

All subjects will be contacted by telephone at 30 days (+/- 2 days) after IMP administration to determine whether any AEs have occurred and to collect information on changes in concomitant medications. Additional study visits will be scheduled if needed for AE management. Any AEs will be followed up until resolution or stabilisation. In case of unanticipated delays in the planned surgical prostatectomy of the Cohort A PCa patients, the follow-up period of such subjects may be extended by up to 2 days to cover the surgery, and/or additional subjects may be enrolled into Cohort A in order to ensure that there are three evaluable subjects in Cohort A (see section 4.10 for criteria of evaluability).

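### On the natural reading of the analysis set, a late or cancelled prostatectomy removes a Cohort A patient from the kinetic and plasma endpoints, which use no surgical specimen

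*Protocol*

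**What the plan says.** Section 4.10 gives three patient criteria in one list:

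- completed scanning sessions I and II with blood and urine collection, whose stated purpose is "to be able to perform kinetic modelling";
- at least one positive lesion on the study scan;
- "Cohort A only: Radical prostatectomy performed within 30 days of the" scan, followed by the concession "In case of a delay of the planned surgery by up to 2 days beyond this 30-day window, a subject may still be considered evaluable".

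The synopsis joins the same three criteria into a single definition of being evaluable for efficacy, but without the 2-day concession.

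Non-evaluability has two consequences. Section 4.10 says "an additional subject may be included in the study to substitute for the non-evaluable subject", and section 6.3 repeats this for delayed surgery: "additional subjects may be enrolled into Cohort A in order to ensure that there are three evaluable subjects in Cohort A". Section 8.2.3 admits to the EAS those who, among other things, "met the scan evaluability criteria set out in section 4.10", and adds: "Statistical analyses for the primary and secondary endpoints (besides safety) will be performed using EAS". No other efficacy set is defined.

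Section 2.4 lists the endpoints concerned. Endpoint 2 compares uptake with histopathology and is already restricted to cases where histopathology exists. Endpoint 3 is "Use of kinetic modelling data to investigate distribution of" the tracer in patients. Endpoint 4 uses the same modelling to improve the imaging protocol. Endpoint 5 is the share of intact tracer in plasma.

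**The concern.** One definition of evaluability serves several endpoints with different data needs. Surgery within the window is needed to relate uptake to the prostate specimen. It is not needed to fit a kinetic model or to measure intact tracer in plasma. Tied to the EAS as it is, the surgical condition also governs endpoints 3 to 5.

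At stake are complete data in a cohort of three. Cohort A is the only cohort defined by primary disease, and the kinetic results are meant to set the imaging protocol for later studies. Sections 3.3, 4.10 and 6.3 all foresee surgical delay, so this is not a remote case. The responses they offer are a 2-day extension and further enrolment, and neither keeps the kinetic data of a patient who misses the window in the analysis.

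**Working it through.** **Planned numbers.** Section 8.1 plans 6 healthy volunteers and 3 patients in each of 3 cohorts: 6 + 3 × 3 = 15 evaluable subjects, which agrees with the stated total. No hypothesis, power or dropout figure is given (8.2.2), so there is no sample-size formula to check.

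**What each endpoint needs.**

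| Endpoint | Inputs according to the protocol | Specimen needed? |
|---|---|---|
| 2, with the Gleason and lesion comparisons (2.4, 7.2.3, 8.2.6) | SUV and histopathology | Yes, for the Cohort A specimen comparison |
| 3 and 4 (2.4, 7.2.2, 8.2.6) | Dynamic PET, lesion uptake, parent tracer in plasma | No |
| 5 (2.4, 7.4) | Blood samples | No |

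Table 3 places all these PET and blood data on the day of injection: imaging ends at 118 min and the last radioactivity blood sample is at 120 min. The urine fractions end at 240 min. Cohorts B and C enter endpoints 3 to 5 with no surgical condition.

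**Tracing one patient.** Take a Cohort A patient with complete scans, blood and urine, a positive lesion, and surgery on day 35.

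1. The window closes at day 30, or at 30 + 2 = day 32 with the discretion in 4.10. Day 35 is outside both.
2. The third criterion of 4.10 fails, so the patient is not evaluable.
3. The EAS rests on 4.10, so the patient is not in the EAS.
4. All non-safety endpoints use the EAS, so the patient is left out of endpoints 2, 3, 4 and 5.
5. The safety set needs only administration of the product, so the primary endpoint is unaffected.

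**Size without replacement.** Cohort A kinetic datasets lost: 1/3 = 33 %. All patient kinetic datasets lost: 1/9 = 11 %. For endpoint 5, which also includes the volunteers: 1/15 = 7 %.

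**Size with one replacement.** Cohort A again has 3 analysed datasets, but 4 complete ones were acquired, so 1/4 = 25 % of the Cohort A kinetic data in hand is left out.

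**How often.** The protocol gives no rate of delay or cancellation. Let q be the assumed chance that a patient who is otherwise complete misses the window, independent between patients. The chance that at least one of the first three is affected is 1 − (1 − q)³. If enrolment continues to three evaluable patients, expected enrolment is 3/(1 − q).

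| Assumed q | At least one of three affected | Expected Cohort A enrolment |
|---|---|---|
| 5 % | 14 % | 3.16 |
| 10 % | 27 % | 3.33 |
| 20 % | 49 % | 3.75 |
| 30 % | 66 % | 4.29 |

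These values of q are illustrations and do not come from the protocol.

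**The case against.** The best counter-argument is textual. Section 8.2.3 speaks of scan evaluability criteria, and prostatectomy is not a scan criterion. Section 8.1 likewise names only the positive lesion before referring to 4.10. On that reading the late-surgery patient stays in the EAS. The ambiguity is real, but 4.10 does not separate scan criteria from others, and the synopsis includes surgery in its definition of evaluable for efficacy. If the narrower reading was meant, the text still needs to say so.

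Second, a specimen confirms that a modelled focus in the prostate is carcinoma, which matters because normal prostate also expresses PSMA (section 1.1). That would be a defensible reason for the rule. The protocol does not give it, every patient already has histologically confirmed cancer, and Cohorts B and C are modelled without surgical confirmation.

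Third, section 8.2.4 says collected data will in general be summarised and listed, and the study is exploratory. So the data need not disappear from the report, but a listing does not put them in the endpoint analysis. Nor is this a detail left to the SAP, because the protocol itself fixes the analysis set.

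Three stronger readings are tempting and are not supported:

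- *Replacement is automatic.* Sections 4.10 and 6.3 only permit it.
- *A substitute's radiation exposure would be avoided.* A substitute supplies a scan paired with a specimen, which is what is missing. The stated 9.2 mSv could still be incurred for that purpose after the fix.
- *Cohort A is selected by scan result.* The synopsis background says that PSMA imaging can inform treatment decisions. Section 1.3, however, says that this study's results will not directly affect patients' treatment. Selection is possible but not shown.

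**Conclusion.** The point holds as a badly fixed analysis-set rule. On the natural reading, a surgical condition relevant only to the histopathology comparison also decides who contributes to endpoints 3, 4 and 5. Each affected patient costs 1 of 3 Cohort A and 1 of 9 patient kinetic datasets if not replaced. If replaced, valid data from a patient already exposed are still left out. How often this would happen is unknown.

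The conclusion assumes that 8.2.3 takes in the whole 4.10 list and that the kinetic and plasma analyses use only the inputs named in 7.2.2, 7.4 and 8.2.6. It concerns the use of data. Safety analysis is untouched, and no clinical rule is in question. The correction is cheap and should be made.

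**What to change.** 1. In 4.10 and the synopsis, make the prostatectomy criterion a condition of evaluability only for the histopathology comparison, that is, endpoint 2 and the related Gleason and lesion comparisons.
2. In 8.2.3, state that endpoints 3 to 5 include every Cohort A patient who meets the scan, blood and urine, and lesion criteria, whether or not surgery takes place and whenever it does. Replace the phrase about scan criteria with wording that says which 4.10 criteria apply to which endpoint.
3. State that a substitute enrolled because of surgical timing serves the histopathology comparison, and that the first patient's kinetic and plasma data are kept.
4. Bring the synopsis and 4.10 into agreement on the 2-day tolerance.

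The cost is wording in three places and possibly different denominators: endpoints 3 to 5 may have more Cohort A patients than endpoint 2. Each table should therefore state its own number of patients.
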